Appendix 5. Analysis Strategy Using a Poisson Model

Poisson Distributions often arise from a Counting process

- Seizure counts as a random variable Y
The expected value of the seizure counts is $E(Y) = \mu$
The variance of the seizure counts is $\text{Var}(Y) = \mu$

Generalized Linear Model for Seizure Counts with equal duration

- $g(\mu) = \ln(\mu) = \alpha + X\beta$
Distribution is Poisson
Link function $g(\mu)$ is the natural log
In other words $\mu = \exp(\alpha + X\beta)$

Incorporating exposure time (T) in the Model

- Off-setting the exposure time by $\ln(T)$
- $\ln(\mu/T) = \alpha + X\beta$
- $\mu = T \cdot \exp(\alpha + X\beta)$
- Adjust for unequal exposure times among treatment groups

Exposure time T is derived in months as study day/28, where study day is derived as the (assessment date-date of start of double blind treatment phase) + 1. Eg, if the subject dropped out at day 26, the exposure time would be 26/28=0.93 months.

The scale parameter will be set to Pearson in the Poisson model.

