6.1.3.2. Number of Seizure-Free Days Gained

The number of seizure-free days gained for each seizure type: PGTC, myoclonic, tonic/tonic, absence, and clonic seizures will be calculated. The number of seizure-free days will be adjusted to a per 12 weeks value (ie, 84 days) for the baseline and 12-week double-blind assessment phases. Changes from baseline are to be computed and the analysis performed accordingly. The 12 week adjusted number of seizure-free days is defined as follows:

number of seizure-free days in a period * 84 / (number of days in a period – number of missing diary days in a period) .

Period refers to the length time in baseline, and in DB. The 12 week adjusted number of seizure-free days will be calculated for baseline and DB; change from baseline will also be calculated.

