7. HANDLING OF MISSING VALUES

Missing data will be handled based on the nature of the endpoint and the proposed statistical methods for analyzing the data.

For all endpoints that include seizure rate, days with missing seizure diary data will be subtracted from the seizure rate calculations. If seizure rate for any phase cannot be calculated for a subject due to missing information, the endpoint that involves seizure rate during that phase will be also missing for that subject.

For scales used in this study, scores will be imputed according to the imputation rules and algorithms for missing component scores that are provided in the data standard documents. Partial dates for AEs and concomitant medications will be imputed according to Pfizer standard algorithms.

The assessment of missing data for the primary endpoint will require the construction of the following windows and drop-out categories:

- *Windowing for each subject will be constructed for the 1st month, 2nd month, and 3rd month the subject was in the study. Thus a 28-day seizure rate will be determined for each windowed month for which seizure data exist, otherwise the seizure data will be considered missing with a corresponding reason for it being missing. Specific details are provided in [Appendix 3](#).*
- *Drop-out patterns will be constructed based on the reason the seizure data is missing for the corresponding windowed month. Hence, the following drop-out patterns will be defined for three specific categories of related to lack of efficacy or adverse event or other reason:*
 - *Completed study as planned.*
 - *Drop-out due to lack of efficacy:*
 - *Drop-out at month 1 due to lack of efficacy;*
 - *Drop-out at month 2 due lack of efficacy;*
 - *Drop-out at month 3 due to lack of efficacy.*
 - *Drop-out due to an adverse event:*
 - *Drop-out at month 1 due to an adverse event;*
 - *Drop-out at month 2 due to an adverse event;*
 - *Drop-out at month 3 due to an adverse event.*
 - *Drop-out due to other reason:*
 - *Drop-out at month 1 due to other reason;*
 - *Drop-out at month 2 due to other reason;*
 - *Drop-out at month 3 due to other reason.*

Other reason includes any drop-outs excluding efficacy and adverse event.

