A supplemental analysis will be performed to investigate generalizability of the treatment difference with respect to the 2 age categories (ie, a possible treatment-by-age interaction that is statistically and clinically relevant). The estimated seizure rate, standard error and the corresponding 95% confidence interval in addition to the treatment difference between each pregabalin treatment group and placebo will be calculated for both pediatric (5-16 years of age) and adult population (17-65 years of age). This supplemental analysis will also be a re-evaluation of the primary analysis model with an interaction term for treatment-by-age. This model will not replace the primary model.

As a supplemental analysis, a generalized linear model assuming a Poisson and negative binomial distributions and canonical log link function will be applied to the raw seizure counts.^{1,2} The model will have an off-set parameter for the amount of time (i.e., $\log_e(\text{days})$) the subject was in the double blind treatment phase. A scale parameter of Pearson will be specified to fit the Poisson distribution.

The analyses with Poisson and negative binomial models will be performed with baseline seizure count as covariate.

The raw 28-day seizure rate will be summarized overall, and separately by age group of pediatrics overall (<17 years) and adults (17-65 years).

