8.5. Summary of Efficacy Analyses

Endpoint (Key Summary Metrics)	Analysis Set	Statistical Method	Model/ Covariates/ Strata	Missing Data	Interpretation
Log _e 28-day PGTC seizure rate (N, LS Mean Diff/SE)	ITT	ANCOVA	Treatment, region, age strata, baseline seizure rate	Days missing from Seizure Diary will be subtracted from rate calculations	Primary Analysis Note: age strata is protocol defined age strata. Baseline is the log of 28-day PGTC rate at baseline
Key summary statistics will be presented for the Log _e 28-day PGTC seizure rate and for the back transformed “percent reduction in seizures” relative to placebo.					
Log _e 28-day PGTC seizure rate (N, LS Mean Diff/SE) (treatment-by-age p-value)	ITT	ANCOVA	Treatment, region, age group, treatment-by-age group interaction, baseline seizure rate	Days missing from Seizure Diary will be subtracted from rate calculations	Supplemental Analysis Note: age groups are Age < 17 yrs and Age ≥ 17 yrs. Baseline is the log of 28-day PGTC rate at baseline.
Key summary statistics will be presented for the Log _e 28-day PGTC seizure rate and for the back transformed “percent reduction in seizures” relative to placebo.					
Responder rate (%)	ITT	Logistic regression	Treatment, region, age strata	Days missing from Seizure Diary will be subtracted from rate calculations	Secondary Analysis
Proportion Seizure-free days (%)	ITT	ANCOVA	Treatment, region, age strata, baseline	Days missing from Seizure Diary will be subtracted from rate calculations	Exploratory Analysis Each seizure type: PGTC, myoclonic, tonic/tonic, absence, and clonic seizures. Baseline for this endpoint is the proportion of seizure free days at baseline.
Number of seizure-free days gained (N, Mean, SE)	ITT	ANCOVA	Treatment, region, age strata, baseline	Days missing from Seizure Diary will be subtracted from rate calculations	Exploratory Analysis Each seizure type: PGTC, myoclonic, tonic/tonic, absence, and clonic seizures. Baseline for this endpoint is the number of adjusted seizure free days at baseline.

Proportion PGTC Seizure-freedom (%)	ITT	Logistic regression	Treatment, region, age strata	Days missing from Seizure Diary will be subtracted from rate calculations	Exploratory Analysis
Log _e 28-day PGTC seizure rate (N, LS Mean Diff/SE)	ITT	ANCOVA	Treatment, region, age strata, baseline	Multiple imputation will be applied.	Sensitivity Analysis. Baseline is the log of 28-day PGTC rate at baseline.

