Log _e 28-day PGTC seizure rate (N, LS Mean Diff/SE)	ITT	ANCOVA	Treatment, region, 2 age groups , baseline	Days missing from Seizure Diary will be subtracted from rate calculations	Sensitivity Analysis Note: age group are Age< 17 yrs and Age>= 17 yrs. Baseline is the log of 28-day PGTC rate at baseline
Log _e 28-day PGTC seizure rate (N, LS Mean Diff/SE)	ITT	ANCOVA	Treatment, pooled region, 2 age groups , baseline	Days missing from Seizure Diary will be subtracted from rate calculations	Sensitivity Analysis Note: age group are Age< 17 yrs and Age>= 17 yrs. US and European Union will be pooled in the region class. Baseline is the log of 28-day PGTC rate at baseline
Change from baseline to double blind phase of Log _e 28-day PGTC seizure rate	ITT	Rank ANCOVA	Treatment, region, age strata, region and ranked log-BL		Sensitivity Analysis (Log-Scale). Baseline is the ranked log of 28-day PGTC rate at baseline.
Change from baseline to double blind phase of Log _e 28-day PGTC seizure rate (DB Phase)	ITT	Wilcoxon-Mann Whitney Test			Sensitivity Analysis (Log-Scale)
Raw Seizure Count	ITT	GENMOD, Poisson and negative binomial distribution with log link	Treatment, and baseline		scale parameter = Pearson for the Poisson model. Baseline for this endpoint is seizure count at baseline.

- All efficacy endpoints will be presented descriptively overall, and separately as by age group of pediatrics overall (<17 years) and adults (17-65 years).

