Appendix 1. Data Derivation Details

This table describes how seizure related endpoints have been defined.

Endpoint	Derivation
8-week baseline phase (b) 28-day seizure rate	28-day seizure rate _b = [(# of seizures _b) ÷ (#of days _b - # of missing diary _b)] × 28, where #of days _b is defined as (first dose date-1) – screening date +1.
12-week double-blind treatment phase (t) 28-day seizure rate	28-day seizure rate _t = [(# of seizures _t) ÷ (#of days _t - # of missing diary _t)] × 28, where #of days _t is defined as date of last dose in phase – date of first dose in phase +1.
Primary endpoint : Log _e of 28-day seizure rate during 12-week double-blind treatment phase	Log _e (28-day seizure rate _t +1)
“Percent reduction in seizures” relative to placebo	
For example, a difference between one of the pregabalin doses and placebo of -0.400 on the log transformed scale for the 28-day seizure rate translates into a 33% reduction in the 28-day seizure rate of the pregabalin group from the placebo group (ie, 100%*[exp-0.400-1] = -33%)
 
An additional back transformation will be calculated for the percent reduction in seizures for each pregabalin treatment group relative to placebo for presentation in the CSR as follows:
 $100\% \times \frac{\exp(\text{LSMean(pregabalin)}) - 1 - [\exp(\text{LSMean(placebo)}) - 1]}{\exp(\text{LSMean(placebo)}) - 1}$
Percent change from baseline in 12-week 28-day seizure rate	% Change = [28-day seizure rate _t - 28-day seizure rate _b] / 28-day seizure rate _b] × 100%
Responders	
≥50% reduction in the 28-day seizure rate from baseline during the 12-week double-blind treatment phase, then response = 1 (responder) otherwise response = 0 (non-responder).
 
The response status will be set as missing if the baseline seizure rate is missing. If baseline seizure rate is non-missing but there are no double-blind phase seizure rates, then the response status will be set as non-response

Proportion Seizure-free days	The numerator for seizure-free days is defined as the number of days the subject experience no seizures over the double-blind assessment phase.

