Number of seizure-free days gained	The number of seizure-free days will be adjusted to a per 12 weeks value (ie, 84 days) for the baseline and 12-week double-blind assessment phases. Changes from baseline are to be computed and the analysis performed accordingly. Number of 12 week adjusted seizure free days is defined as follows: Number of seizure free days in a period x 84 / number of days in a period.
Proportion PGTC Seizure-freedom	The numerator for seizure-freedom is defined as the number of subjects that experience no PGTC seizures over the last 28 days of the double-blind assessment phase (Patient must have received at least 42 days (2 weeks + 28 days) of study medication and have a minimum of 21 of the last 28 days as non-missing diary). The denominator is the ITT population with 42 days (2 weeks + 28 days) of study medication.

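### The count-model offset ignores missing diary days, and Appendix 1 contradicts Section 6.1.3.2 on the denominator for seizure-free days gained

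*SAP*

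**What the plan says.** **Count models.** Section 8.1 plans, as a supplemental analysis, Poisson and negative binomial models for raw seizure counts. On exposure it says "The model will have an off-set parameter for the amount of time" the subject spent in the double-blind phase, entered as log days. Appendix 5 makes this specific: "Exposure time T is derived in months as study day/28", where study day is an assessment date minus the start of double-blind treatment, plus one. In the Section 8.5 row headed "GENMOD, Poisson and negative binomial distribution with log link", the missing-data entry is blank.

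**Primary rate.** Section 6.1.1 and Appendix 1 divide the seizure count by days in the phase less missing diary days. Appendix 1 defines days in the phase as "date of last dose in phase – date of first dose in phase +1". Section 7 gives the general rule: "For all endpoints that include seizure rate, days with missing seizure diary data will be subtracted from the seizure rate calculations".

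**Seizure-free days gained (exploratory).** Section 6.1.3.2 scales to 84 days using the denominator "number of days in a period – number of missing diary days in a period". The Section 8.5 row for this endpoint agrees: "Days missing from Seizure Diary will be subtracted from rate calculations". Appendix 1 instead gives "Number of seizure free days in a period x 84 / number of days in a period".

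**The concern.** A missing diary day is a day on which seizures were not observed. The primary rate treats it that way; the count-model offset treats it as exposure. If seizures enter the count only from completed diary days, the offset understates each subject's rate by that subject's missing fraction. The rate ratio is then biased whenever diary completeness differs by arm, in either direction. These models are meant to support the primary result on the same seizures, so a disagreement with the ANCOVA might reflect only the denominator. The end dates also differ: Appendix 5 runs to an unspecified assessment date, Appendix 1 to the last dose in the phase.

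For seizure-free days gained, the SAP holds two formulas that disagree for every subject with a missing diary day. Appendix 1 is the derivation table, so a programmer may well code from it. Two live formulas also leave a choice that could be made after unblinding.

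**Working it through.** The documents give no missing-diary fractions, so every missingness level below is an assumption.

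**Plan's own figure.** Appendix 5 has a subject dropping out at day 26: 26/28 = 0.929, which rounds to the stated 0.93 months. Net of 3 missing diary days it would be 23/28 = 0.82; net of 6, 20/28 = 0.71.

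**Offset.** Let D be days in the phase, M missing diary days, m = M/D and λ the true daily rate. If seizures are counted only on diary days, the expected count is λ(D − M). An offset of log D then estimates λ(D − M)/D = λ(1 − m), so

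estimated ratio = true ratio × (1 − m_active)/(1 − m_placebo).

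| Missing, active / placebo | Factor | Log shift | Share of 0.358 |
|---|---|---|---|
| equal | 1.000 | 0 | 0% |
| 10% / 5% | 0.90/0.95 = 0.947 | −0.054 | 15% |
| 15% / 5% | 0.85/0.95 = 0.895 | −0.111 | 31% |
| 5% / 10% | 0.95/0.90 = 1.056 | +0.054 | 15% |
| 5% / 15% | 0.95/0.85 = 1.118 | +0.111 | 31% |

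The 0.358 is the planned Dose Level 1 difference (Section 2.2). It is only a rough yardstick, because it lies on the log(rate + 1) scale. At the 10% / 5% factor, a true ratio of exp(−0.358) = 0.699 would read 0.662.

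A simulation checked that the factor carries over to the fitted models. It used 400 runs with 56 per arm, lognormal rates with median 3 per 28 days and log SD 0.8, gamma overdispersion, beta-distributed missing fractions and baseline count as covariate. The elapsed-time estimate divided by the diary-day estimate, for Pearson-scaled Poisson and for negative binomial (dispersion fixed at 0.6), was:

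- 5% active, 5% placebo: 0.999 and 1.000
- 10% active, 5% placebo: 0.947 and 0.947
- 15% active, 5% placebo: 0.894 and 0.895
- 5% active, 10% placebo: 1.055 and 1.055

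This confirms the algebra; it is not evidence that missingness will differ.

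Section 8.1 states the offset in days and Appendix 5 in months. That moves only the intercept, by ln 28 = 3.33, and leaves the rate ratio unchanged.

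**Seizure-free days, one subject.** Take 70 seizure-free days with 8 of 84 diary days missing.

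- Section 6.1.3.2: 70 × 84/76 = 77.4. This is 84 times the Section 6.1.3.1 proportion, 70/76 = 92.1%.
- Appendix 1: 70 × 84/84 = 70.0, equivalent to 70/84 = 83.3%.

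**Seizure-free days, treatment contrast.** The endpoint is change from baseline. Assume seizure-free proportions of 0.85 at baseline, 0.88 on placebo and 0.91 on active, with 5% missing at baseline in each arm, so the baseline terms cancel.

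- Section 6.1.3.2: 84 × (0.91 − 0.88) = 2.52 days, whatever the missingness.
- Appendix 1, missing days not credited as seizure-free: 84 × [0.91(1 − m_a) − 0.88(1 − m_p)].
  - 5% in both arms: 84 × 0.95 × 0.03 = 2.39
  - 10% in both arms: 84 × 0.90 × 0.03 = 2.27
  - 10% active, 5% placebo: 84 × (0.819 − 0.836) = −1.43
  - 5% active, 10% placebo: 84 × (0.8645 − 0.792) = 6.09
- Appendix 1, missing days credited as seizure-free (add m to each arm's term):
  - 10% active, 5% placebo: 84 × (0.919 − 0.886) = 2.77
  - 5% active, 10% placebo: 84 × (0.9145 − 0.892) = 1.89

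**The case against.** The offset is not a strict contradiction. Section 7's rule is worded for endpoints that include a seizure rate, while the count models analyse raw counts, and elapsed time is a common offset. That stands: the rule reaches the offset by intent, not by its wording. The blank missing-data entry is weak evidence, since the rank ANCOVA and Wilcoxon rows are blank too.

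The bias also depends on a fact the available text does not settle. If seizures on days without a diary entry reach the count by another route, elapsed time could be the right exposure. But the same argument would count against the plan's own primary denominator. Having treated those days as unobserved in the primary rate, the plan should do so here or explain the difference.

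The end-date difference may be only loose wording. Appendix 5 repeats the study-day definition of Appendix 3, and its example runs to the drop-out day. No size is claimed for it.

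For seizure-free days gained, the intended rule can be recovered from Sections 6.1.3.2 and 8.5, and Appendix 1 looks like a row that was not brought into line. The shorthand reading fails, however: Section 6.1.3.2 uses the same phrase for gross days and then subtracts missing days from it.

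The large shifts (−1.43 and 6.09) need both unequal missingness and missing days not credited as seizure-free. Nothing in the documents suggests that completeness will differ by arm. That too stands.

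**Conclusion.** Both parts hold, at different strength. Appendix 1 is wrong as written for seizure-free days gained, because it conflicts with two other current statements and changes the value for any subject with a missing diary day. The offset is an unexplained inconsistency with the primary rate.

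The consequences are confined to a supplemental and an exploratory analysis. With equal missingness the rate ratio is unbiased, and the seizure-free-days contrast moves by only 0.13 to 0.25 days in the example. With a five-point difference between arms (5% against 10%), the rate ratio shifts by a factor of 0.947 or 1.056. The illustrative 2.52-day contrast then becomes −1.43 or 6.09 if missing days are not credited, and 2.77 or 1.89 if they are. The text comparison is firm; these sizes are conditional on the assumed missingness and proportions and, for the offset, on seizures being recorded only on diary days. The item should be corrected, but it does not threaten the main conclusion.

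**What to change.** 1. In Section 8.1, the raw-count row of Section 8.5 and Appendix 5, define the offset as the log of days in the phase less missing diary days. Use the same start and end dates as the primary denominator in Appendix 1. State whether seizures on days without a diary entry can enter the count.
2. In Appendix 1, replace the denominator for seizure-free days gained with the one in Section 6.1.3.2, and state that missing days are not counted as seizure-free.

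The cost is SAP wording and programming only; the required denominator is already derived for the primary endpoint. SAP Section 1 records the study as ongoing and blinded when the amendments were made, so at that stage the change could be pre-specified.

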Appendix 6. Blinded Sample Size Re-Estimation

The proposed sample size re-estimation formula (Friede and Keiser, 2011)³ is the following:

$$n^* = \frac{(1+\gamma)^2 \cdot (z_{1-\alpha/2} + z_{1-\beta})^2 \cdot (1-\rho^2) \cdot \sigma^2}{\gamma \Delta^2}$$

where,

n^* is the revised total sample size of two treatment groups for this estimation;

γ is the ratio of the estimated sample size of two treatment groups;

$z_{1-\alpha/2}$ is a percentile from a standard normal cdf with $\alpha/2=0.025$;

$z_{1-\beta}$ is a percentile from a standard normal cdf with $\beta=0.20$;

σ^2 is the blinded estimate of pooled variance for outcome variable at the interim review;

ρ is the blinded estimate for the correlation between an outcome and a covariate variable;

Δ is the clinically meaningful difference between *Dose Level 1: pregabalin 5 mg/kg/day (maximum 300 mg/day)* and placebo (i.e., 0.358) as specified in the protocol.

For this study, the ratio of estimated sample size of two treatment group (γ) is assumed as one due to 1:1 randomization with respect to placebo versus dose level 1. In addition, the estimates for correlation (ρ) and pooled variance (σ^2) is estimated based on the residual variance of ANCOVA. Therefore, the simplified equation for this study is:

$$n^* = \frac{4 \cdot (z_{1-\alpha/2} + z_{1-\beta})^2 \cdot \tilde{s}^2}{\Delta^2}$$

where,

\tilde{s}^2 is the blinded estimate of the residual variance based on ANCOVA at the interim review.

The pooled blinded estimate of the variance, \tilde{s}^2 , will be based in a blinded manner without making any correction for possible treatment group differences after the 1st 110 subjects have had the opportunity to complete the study. Since baseline 28 day seizure rate, age strata, and geographical region are important pre-specified modeling terms that explain sources of variability in the data, the estimate \tilde{s}^2 will take into consideration these three modeling terms as the mean squared error. While this pooled

estimate of the variance under the null hypothesis will be biased upwards, this bias is negligible when the overall sample is reasonably large. Results from a thorough simulation study indicated that the re-estimated sample size using the uncorrected pooled variance required only 2 -to-3 more subjects per group relative to using a corrected pooled variance estimate. The proposed blinded sample size re-estimation procedure will only allow for a new sample size (n_{New}) to be increased beyond the initial targeted sample size (n_{Initial}), but not beyond the pre-determined maximum sample size ($n_{\text{Max}}=195$).
